5.1.3 Laboratory Evaluations

With the exception of drawing a lidocaine level in the event of a serious adverse event, blood work is not part of the study. Any abnormal labs thought to be due to the study drug will be recorded if labs were ordered as standard of care, provided they were drawn after the study drug was administered. Pregnant patients cannot be enrolled and whichever pregnancy test is used in their standard of care workup will be used to determine eligibility for the study. Women of childbearing age presenting to the emergency department with abdominal pain nearly universally have a pregnancy test measured at ED presentation as standard of care to evaluate for pregnancy or ectopic pregnancy.

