4.2 Study Intervention

4.2.1 Time Zero

- Pain score (1-10)
- Patient placed on monitor
- Vital signs recorded (heart rate, respiratory rate, systolic blood pressure, diastolic blood pressure, pulse oximetry, source of oxygen)
- Study drug administered by patient's nurse (mixed by research pharmacist and sent to the nurse) over 5 minutes

4.2.2 15 minutes after the study drug was started (not after it finished), up to a 15 minute delay will be tolerated

- Pain score
- Vital Signs (same as above)
- Recording of any new symptoms (classified at this point as adverse events)
- Recording of sufficient pain relief (yes or no)
- Recording of any medications to treat adverse events (yes or no). If yes, document was medication was administered, why, and when.
- Recording on whether or not naloxone has been administered (yes or no)
- Recording of any change in disposition thought to be due to study drug (yes or no)
- Recording of any serious adverse event (yes or no)

4.2.3 30 minutes after the study drug was started (not after it finished), up to a 15 minute delay will be tolerated

- Pain score
- Vital Signs (same as above)
- Recording of any new symptoms (classified at this point as adverse events)
- Recording of sufficient pain relief (yes or no)
- Recording of any medications to treat adverse events (yes or no)
- Recording on whether or not naloxone has been administered (yes or no)
- Recording of change in disposition thought to be due to study drug (yes or no)
- Recording of any serious adverse event (yes or no)

4.2.4 60 minutes after the study drug was started (not after it finished), up to a 15 minute delay will be tolerated

- Pain score
- Vital Signs (same as above)
- Recording of any new symptoms (classified at this point as adverse events)
- Recording of sufficient pain relief (yes or no)
- Recording of any medications to treat adverse events (yes or no)
- Recording on whether or not naloxone has been administered (yes or no)
- Recording of change in disposition thought to be due to study drug (yes or no)
- Recording of any serious adverse event (yes or no)

4.2.5 90 minutes after the study drug was started (not after it finished), up to a 15 minute delay will be tolerated

- Pain score
- Vital Signs (same as above)
- Recording of any new symptoms (classified at this point as adverse events)
- Recording of sufficient pain relief (yes or no)

- Recording of any medications to treat adverse events (yes or no)

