5.2 Safety Evaluation

Subject safety will be monitored by serious adverse events, reported adverse events, vital signs, physical examinations, laboratory data (obtained through standard care), and medications required to treat any adverse events thought to be due to the study drug. In the event of any serious adverse event, a lidocaine level will be drawn on the patient.

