6.2 Secondary Endpoints

Secondary endpoints will include the following:

- The mean pain improvement at time 15, 30, 60, 120, 150 and 180 minutes (using same test as primary end point).

- Difference in proportion of patients with adverse events, who experience serious adverse events, require medication to treat adverse events, report insufficient pain relief, require naloxone, have a change in disposition, and a missed diagnosis will be evaluated using a Chi-Square test with an alpha level of 0.05.
- Proportion of patients who prefer to receive the same drug at a future visit will be compared as proportions using a Chi-Square test with an alpha level of 0.05.

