8.2 Adverse Event Reporting

Unanticipated problems related to the research involving risks to subjects or others that occur during the course of this study and SAEs will be reported to the IRB in accordance with IRB Attachment EEE: Prompt Reporting Guidelines. AEs that are not serious but that are notable and could involve risks to subjects will be summarized and submitted to the IRB at the time of continuing review. Abnormal blood work will only be reported as an adverse event if it was drawn after the patient received the study medication and is a departure from baseline lab work.

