8.3 Definition of an Adverse Event

An adverse event is any untoward medical occurrence in a subject receiving a test article and which the occurrence does not necessarily have a causal relationship with the treatment. An adverse event can therefore be any unfavorable and unintended sign (including an abnormal laboratory finding), symptom, or disease temporally associated with the use of the test article, whether or not related to the product.

All AEs (including SAEs) will be noted in the study records and on the case report form with a full description including the nature, date and time of onset, determination of non-serious versus serious, intensity (mild, moderate, severe), duration, causality, and outcome of the event.

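### Section 5.1.3 screens post-dose abnormal labs by suspected cause, while 8.3 counts them as adverse events whatever the cause, so the lab part of the adverse-event endpoint has two incompatible capture rules

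*Combined protocol and SAP*

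**What the plan says.** **Laboratory abnormalities.** Three places bear on whether a post-dose abnormal result becomes an adverse event.

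- Section 5.1.3: "Any abnormal labs thought to be due to the study drug will be recorded if labs were ordered as standard of care", provided the sample was taken after dosing.
- Section 8.2: "Abnormal blood work will only be reported as an adverse event if it was drawn after the patient received the study medication" and differs from baseline. Cause is not mentioned.
- Section 8.3: an adverse event is any unfavourable sign, "including an abnormal laboratory finding), symptom, or disease temporally associated with the use of the test article, whether or not related to the product". It adds: "All AEs (including SAEs) will be noted in the study records and on the case report form", with causality among the items to be described.

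**Medications for adverse events.** Section 5.2 lists what is used to monitor safety and includes "medications required to treat any adverse events thought to be due to the study drug". The timed forms in 4.2.2 to 4.2.8 ask about any medication for adverse events, with no causal condition. Section 6.2 tests the proportion of patients who "require medication to treat adverse events", again without one.

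**Analysis.** Section 6.2 compares the proportion with adverse events, and the proportion needing medication for them, by chi-square at 0.05. Section 6.2.4 tabulates adverse events by type. The objective in 2.2 speaks instead of side effects, a term that can be read as causal.

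**The concern.** A capture rule and a causality assessment do different jobs. If everything that meets the definition is captured and then judged for cause, both an all-cause and a related-only count can be made, and the judgement can be reviewed. If suspected cause decides whether the result is written down at all, only the filtered count survives. A result omitted as unrelated leaves no adverse-event entry to re-examine after unblinding.

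Section 5.1.3 puts the judgement first; 8.3 puts it after. Two staff members following different sections would record the same result differently, and the plan does not say who judges cause under 5.1.3 or by what criteria. The adverse-event proportion in 6.2 and the by-type table in 6.2.4 both inherit that ambiguity.

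**Working it through.** There is no planned figure to reproduce: the sample size in 6.3 is built on the pain score and is unaffected. The check is a comparison of the texts, followed by a bound on what the lab rule can change.

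**Step 1: one case under each lab rule.** Take a standard-care result drawn after dosing that is abnormal, differs from baseline, and is thought to come from the illness.

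| Section | Condition on cause | Outcome |
|---|---|---|
| 5.1.3 | must be attributed to the study drug | no instruction to record |
| 8.2 | none stated | not ruled out |
| 8.3 | expressly irrelevant | adverse event, entered on the form with causality |

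Sections 5.1.3 and 8.3 give different outcomes. Section 8.2 does not settle the matter, because its conditions are necessary ones and it does not address cause. No other section says which rule governs.

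**Step 2: the same test for medications.** Take a drug given for an adverse event thought to come from the illness. Section 4.2 records it and 6.2 counts it. Section 5.2 leaves it off a list of monitoring inputs but sets no endpoint rule. Collection and analysis agree, so the tested endpoint has one rule. Section 5.2 also lists laboratory data without a causal condition, so the lab filter stands in 5.1.3 alone.

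**Step 3: how far the lab rule can move the tested proportion.** The endpoint is binary per patient. A patient with any other adverse event is already counted. The two rules therefore differ in an arm by

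(patients whose only adverse event is a post-dose abnormal lab judged unrelated) ÷ (patients in the arm).

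With 187 patients split 94 and 93, each such patient moves the proportion by 1/94 = 1.06 or 1/93 = 1.08 percentage points; with the 85 per arm of 6.3, by 1/85 = 1.18 points. The number of such patients is not derivable from the documents. Two features keep it low: under 5.1.3 blood tests are outside the study procedures, except a lidocaine level after a serious event, so only standard-care samples count; and new symptoms are recorded without attribution at every assessment from 15 to 180 minutes. The by-type table in 6.2.4 is more exposed, since there each lab event can appear even in a patient who has other events.

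**The case against.** The strongest reply is that 5.1.3 never says that other abnormal labs are *not* recorded, so 8.3 could be read as covering the rest. That is a possible reading, but it leaves the causal condition in 5.1.3 with no function, and 5.1.3 is the section staff would consult about labs. The ambiguity remains.

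It can also be said that patient, nurse and physician are blinded (3.1), so the filter need not favour an arm. This stands in large part. Section 9.4.2 describes a recognisable course of lidocaine symptoms, but the documents describe no laboratory signature for either drug. Allocation-dependent attribution of labs is possible and not shown.

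A reader might go further in three ways.

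- *That two tested endpoints have conflicting rules.* The medication endpoint does not; 4.2 and 6.2 agree, and 5.2 is a monitoring list.
- *That the choice of rule swings the result.* Suppose drug-caused treatment occurs in 15% v 5% (94 and 93 patients). Power is then 64%, and it falls to 35%, 23% or 17% when independent illness-related treatment of 10%, 20% or 30% is added to each arm. These rates are invented, and they concern the medication endpoint, where no rule conflict exists. Likewise, with equal any-cause rates of 20% to 40% and 80% v 50% of events attributed to drug, a fully filtered endpoint at 85 per arm would show a difference about 21% to 43% of the time. But only the lab component is filtered here, and the unequal attribution is assumed.
- *That reasons for treatment after 15 minutes are lost.* The later forms ask only yes or no, but 8.3 separately requires a full description, including causality, of every adverse event.

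Finally, the term side effects in 2.2 may favour a related-only count. That is fair, and is why the fix keeps such a count in support.

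**Conclusion.** The point holds for laboratory abnormalities: 5.1.3 and 8.3 give incompatible capture rules for one component of the adverse-event proportion tested in 6.2, and the 5.1.3 rule screens by opinion before causality is recorded. For treatment medications, the phrase in 5.2 is a consistency correction only.

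The size is probably small, about one percentage point per affected patient in an arm, and the number affected cannot be estimated because the documents give no rates. This rests on reading 5.1.3 as a condition for recording, and on standard-care labs being the only source. The documents do not support a claim that the filter biases the comparison between arms or decides its significance. The primary endpoint is untouched.

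**What to change.** 1. In 5.1.3, delete the causal condition. Record as an adverse event each abnormal standard-care result drawn after dosing that differs from baseline, in line with 8.2 and 8.3.
2. In 5.2, delete the same condition on medications, so that the list matches 4.2 and 6.2.
3. In 8.3, state that causality is judged after capture, by a named role still blinded to allocation, and never decides entry. Section 8.3 asks for causality but gives no scale and does not mention blinding, and the terms in 8.4.1 are given for serious events only; extending them to all adverse events would suffice.
4. In 6.2, state that the adverse-event and treatment-medication proportions count events regardless of cause. Add a supportive table limited to events judged related before unblinding, which serves the side-effect wording of 2.2.

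The cost is a few lines of text and a few more adverse-event entries. The downside is that the all-cause counts will include some illness-related events, which dilute the comparison; the supportive table shows the related events separately.

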5.1.4 Other Evaluations, Measures

EKG's will be performed on all patients the day of their presentation to the emergency department and prior to them being allowed to participate in the study as an EKG with an abnormal interval would exclude them from the study.

5.2 Safety Evaluation

Subject safety will be monitored by serious adverse events, reported adverse events, vital signs, physical examinations, laboratory data (obtained through standard care), and medications required to treat any adverse events thought to be due to the study drug. In the event of any serious adverse event, a lidocaine level will be drawn on the patient.

6 STATISTICAL CONSIDERATIONS

6.1 Primary Endpoint

The primary endpoint is mean improvement in pain score, defined as the difference between pain score at the beginning of the study drug infusion (time zero) and 90 minutes after the study drug was administered (time zero). The mean pain improvement will be compared between each study drug using a two tailed t-test with an alpha level of 0.05 and confidence interval.

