Study Duration	Each subject's participation will last one week. The entire study is expected to last twelve months.
Study Phases Screening	This study will have three phases. Screening and intervention will occur on the same day in the emergency department. Follow up will occur 7 days later.

Intervention	
Follow-Up	
Efficacy Evaluations	The primary outcome for this study will be mean pain score improvement after 90 minutes from administration of study drug.
Pharmacokinetic Evaluations	Not applicable
Safety Evaluations	Patient reported side effects, medications required to treat side effects, administration of naloxone, change in disposition attributed to study drug and incidence of any serious adverse events.
Statistical And Analytic Plan	Intention to treat. Statistical analysis will be primarily t-tests and chi-square tests.
Data And Safety Monitoring Plan	A DSMB will be in place.

TABLE 1: SCHEDULE OF STUDY PROCEDURES

TABLE 1: SCHEDULE OF STUDY PROCEDURES (CONTINUED)

FIGURE 1: STUDY DIAGRAM

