1.3 Selection of Drugs and Dosages

Lidocaine (NDC 0338-0411-02) will be dosed at 2 mg/kg and given intravenously over 5 minutes. Hydromorphone (NDC 0409-1283-31) will be given at a dose of 1 mg, intravenously over 5 minutes. These are the maximum daily doses for each medication under this protocol,

however more hydromorphone can be given at the discretion of the treating provider if the patient has insufficient analgesia.

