2.1 Primary Objective (or Aim)

The primary objective of this study is to determine whether intravenous lidocaine dosed at 2 mg/kg has equal analgesic efficacy as intravenous hydromorphone at 1 mg, as measured by the improvement in pain score after 90 minutes following administration of study drug.

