4.5 Rescue Medication Administration

If at any point the patient expressed inadequate analgesia and the treating provider wants to administer a new pain drug, they will be eligible to do so however that will be marked as “Insufficient pain relief”. The patient can continue with the study unless at any point they wish to withdraw. Rescue medication will be administered at the discretion of the treating physician or advance practice provider. Rescue medication will not be lidocaine and will never be given to a patient more than once in this study.

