6.2.2 Efficacy Analysis

The primary outcome will be assessed using a two-tailed t-test using an alpha level of 0.05. A 95% confidence interval will be recorded for each mean. The same test will be used for all numerical pain outcomes. All other tests will use a chi-square test with an alpha level of 0.05 and confidence interval of 95%.

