9.4.4 Risk-Benefit Assessment

As stated above, there are minimal risks for participating in this study. While patients will not directly benefit from participating in this study, future patients can benefit if lidocaine has equal analgesic efficacy as hydromorphone. Essentially, it would minimize the need for narcotics to treat acute abdominal pain in the emergency department.

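### The 90-minute primary comparison includes relief from rescue, which may be hydromorphone, so on its own it cannot show that lidocaine itself equals hydromorphone

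*Combined protocol and SAP*

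**What the plan says.** The primary endpoint (section 6.1) is the change in pain score from time zero to 90 minutes: "The mean pain improvement will be compared between each study drug using a two tailed t-test". Section 6.2.2 repeats the test: "The primary outcome will be assessed using a two-tailed t-test using an alpha level of 0.05". The synopsis gives the analysis principle: "Intention to treat. Statistical analysis will be primarily t-tests and chi-square tests".

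Rescue is described in two places. Section 1.3, after stating the protocol doses, adds: "however more hydromorphone can be given at the discretion of the treating provider if the patient has insufficient analgesia". Section 4.5 opens: "If at any point the patient expressed inadequate analgesia and the treating provider wants to administer a new pain drug". It lets the provider do so, marks the patient as having insufficient relief, and rules out lidocaine as the rescue drug. It then says: "The patient can continue with the study unless at any point they wish to withdraw". Under section 3.1 the patient, nurse and physician are blinded, so rescue is decided without knowledge of the arm.

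The question to be answered is in section 2.1: whether lidocaine at 2 mg/kg "has equal analgesic efficacy as intravenous hydromorphone at 1 mg, as measured by the improvement in pain score after 90 minutes". Section 9.4.4 gives the hoped-for benefit of equal efficacy: "it would minimize the need for narcotics to treat acute abdominal pain in the emergency department".

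Section 6.2 plans a chi-square test on insufficient relief, and t-tests on pain at 15, 30, 60, 120, 150 and 180 minutes. The only substitution rule, in section 4.4, covers missed numerical secondary outcomes. A score taken after rescue is not a missed score.

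**The concern.** Rescue can be the comparator drug and can never be the test drug. If lidocaine relieves pain less well, more lidocaine patients are likely to be rescued, some of them with hydromorphone before the 90-minute score. Their later relief then counts in the lidocaine mean. The two means move together, towards the equality the trial hopes to find.

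A rescue imbalance is plausible but not certain. Section 1.2 reports that in the group's earlier trial a fixed 120 mg dose of lidocaine (about 1.5 mg/kg) improved pain by 3.8 points against 5 for hydromorphone. The present dose is higher.

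What is at stake is the reading of a similar result. It could mean that lidocaine works as well as hydromorphone, or that lidocaine more often failed and hydromorphone made up the difference. The second reading is the opposite of the narcotic-sparing benefit in section 9.4.4, and the primary result alone cannot tell the two apart.

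**Working it through.** **1. What the plan implies.** The synopsis says intention to treat, section 4.5 keeps rescued patients in the study, and section 6.1 makes no exception for rescue. Together these imply that the observed 90-minute score is used whether or not rescue came first. No section says so outright.

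**2. The plan's own sample size.** Inputs from section 6.3: difference 1.3, SD 3, two-sided alpha 0.05, power 80%. The t-based solution is 84.57, so 85 per arm, as stated. Then 2 × 85 = 170 and 170 × 1.10 = 187, also as stated. The calculation makes no separate allowance for rescue.

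**3. Size of the shift.** Let pL and pH be the proportions rescued in time to affect the 90-minute score on lidocaine and hydromorphone, and g the points rescue adds by then, taken as equal in both arms.

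Observed difference = true difference − g × (pL − pH)

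For each 10-percentage-point excess on lidocaine:
- g = 2: 2 × 0.10 = 0.2 points
- g = 5: 5 × 0.10 = 0.5 points
- equal rescue proportions: no shift

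**4. Effect on power, by simulation.** There were 20,000 trials per setting, with 85 per arm. Improvement without rescue is normal: lidocaine mean 3.7 (SD 3.1), hydromorphone mean 5.0 (SD 2.9). The SDs are from section 6.3, the mean of 5 is from section 1.2, and 3.7 = 5.0 − 1.3. A fraction f of patients whose improvement is below a threshold is rescued in time and gains g. The values of f, the threshold and g are assumed.

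| f | Threshold | Rescued, lidocaine v hydromorphone | g | Difference | Power |
|---|---|---|---|---|---|
| none | – | 0% v 0% | – | 1.30 | 80% |
| 0.5 | 1.3 | 11% v 5% | 2 | 1.18 | 78% |
| 1 | 1.3 | 22% v 10% | 2 | 1.06 | 76% |
| 0.5 | 2 | 15% v 8% | 4 | 1.02 | 70% |
| 1 | 2 | 29% v 15% | 4 | 0.74 | 59% |
| 0.5 | 3 | 21% v 12% | 5 | 0.89 | 58% |
| 1 | 3 | 41% v 25% | 5 | 0.47 | 35% |

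For example, the first rescue row is 1.3 − 2 × (0.11 − 0.05) = 1.18. Proportions are rounded, so other rows agree with the formula only approximately.

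With g = 2, power stays at about 75–78% in all six combinations of f (0.5, 1) and threshold (1.3, 2, 3). It falls less than the difference alone would suggest because rescuing poor responders also narrows the spread of scores. Holding the SD at 3 gives lower power: with 30% v 20% rescued and g = 2, the difference is 1.3 − 2 × 0.10 = 1.10 and power is 67%. That ignores the narrowing, so it too is a stronger assumption.

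**5. Sensitivity to the means.** The earlier trial allowed a repeat dose (section 1.2.2.2), so its mean of 5 may already include re-treatment. Repeating the six tabulated rescue settings with 4.0 and 2.7 gives differences of 1.15 to 0.87 and power of 77% to 53% for f = 0.5. For f = 1 it gives 1.00 to 0.43 and 77% to 33%. The SDs were left unchanged, although they may carry the same re-treatment.

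**The case against.** The strongest reply is that the plan is sound as it stands. Intention to treat with rescued patients kept in is a standard comparison, and the handling of their scores can be inferred. Need for other pain medication is already a secondary outcome (section 2.2), is tested between arms (section 6.2) and is recorded at each timed assessment (section 4.2). Pain is also compared at 15, 30 and 60 minutes, when fewer patients can have been rescued. Rescue is open to both arms under blinding and need not be hydromorphone. Section 4.5 can also be read as limiting it to one dose.

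Most of this stands. A reader might infer that the primary test is invalid, or that the treatment of rescued patients is wholly undefined. The documents do not support either reading. A reader might also take the 35–59% power figures as expected losses. They are not: they need gains of 4 or 5 points, and 5 points is the full mean hydromorphone effect from the earlier trial, credited even to patients who have just responded poorly to hydromorphone. Nor can one say that the rescue drug and time go unrecorded, because the contents of Table 1 are not visible in the text available.

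What the reply does not remove is the gap between the test and the claim. The secondary results can reveal a rescue imbalance, but they leave the primary estimate as it is. Section 6.2 does not tie insufficient relief to the first 90 minutes, although recording runs to 180.

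**Conclusion.** The concern holds in a limited form. The primary t-test is valid for comparing strategies that include rescue. By itself it cannot support the section 2.1 conclusion that lidocaine equals hydromorphone, because excess hydromorphone rescue on lidocaine would push the result towards that conclusion.

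The shift is g times the excess rescue proportion. It requires more rescue before 90 minutes on lidocaine, and the formula assumes the same gain in both arms. With no rescue rate or rescue effect in the documents, its actual size cannot be given. A 2-point gain costs a few percentage points of power in the simulation, and larger losses depend on stronger assumptions. The plan should be changed on this point, but it is not a fatal flaw. The absence of an equivalence or non-inferiority margin is a separate matter that this change does not solve.

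**What to change.** Amend section 6 before unblinding:

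1. Keep the t-test on all 90-minute scores as primary. State that scores after rescue are used as observed and that it compares strategies including rescue.
2. Prespecify one supportive analysis in the same patients as the primary analysis. For anyone rescued before 90 minutes, use the last scheduled pain score before rescue. Sections 4.4 and 4.6.1 already remove some patients (early leavers from timed scoring, withdrawals from analysis), so the two patient sets should be kept identical.
3. Report the proportion rescued by 90 minutes in each arm beside the primary result.
4. State that equality of lidocaine alone with hydromorphone will not be concluded from the all-scores result alone.
5. Record the rescue drug and clock time, if Table 1 does not already provide for them.

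The cost is one paragraph and at most one or two data fields, with no extra patients or visits. Pain and sufficient relief are already recorded at 15, 30, 60 and 90 minutes. The drawback is that pre-rescue scores mix time points and may miss a late drug effect, so this analysis can only be supportive.
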